**CONFIDENTIAL**

205724

Procedure	Pre-Screening a (Visit 0)	Screening a (Visit 1)	Study Visits									Early Withdrawal	Follow Up  (up to 28 days post last dose)
			2	3	4	5	6	7	8	9	10		
Study Day			-7	1	14	28	56	84	112	140	168		
Assessment Window	-30 d		± 0d	+ 3d	± 3d	± 3d	± 3d	± 3d	± 3d	± 3d	± 3d		
Participant Global Impression of Activity Limitation			X										
Participant Impression of Change in Activity Limitation					X	X	X	X	X	X	X	X	
Genetic, Pharmacokinetic and Biomarker Blood Collections													
Blood sample for Genetics				X									
Blood sample for pharmacokinetics (PK) m				X			X	X			X		
Blood sample for Fibrinogen				X				X			X	X	
Blood sample for CRP				X				X			X	X	
Blood Sample for Exploratory Biomarkers				X				X			X	X	

Procedure	Pre-Screening a (Visit 0)	Screening a (Visit 1)	Study Visits									Early Withdrawal	Follow Up  (up to 28 days post last dose)
			2	3	4	5	6	7	8	9	10		
Study Day			-7	1	14	28	56	84	112	140	168		
Assessment Window	-30 d		± 0d	+ 3d	± 3d	± 3d	± 3d	± 3d	± 3d	± 3d	± 3d		

a. Pre-screening and screening visits may be completed on the same day.
 
b. Agreeing to the genetic sample consent is not required for study participation.
 
c. A pre-screening plasma fibrinogen measurement is only required for participants with 1 COPD exacerbation in the prior year.
 
d. Smoking status /history assessed at screening: smoking status rechecked at Visit 2
 
e. Includes substance usage, past and present medical conditions and family history of premature CV disease.
 
f. See inclusion/exclusion criteria for CXR screening requirement
 
g. Hepatitis B (HBsAg) and Hepatitis C (HepC antibody) testing is required. If testing otherwise performed within 3 months prior to the first dose of study treatment, testing at screening is not required. Hepatitis C RNA testing is optional; however a confirmatory negative Hepatitis C RNA test must be obtained, to be able to enrol participants with positive Hepatitis C antibody due to prior resolved disease.
 
h. Participant’s clinical status should be reviewed.
 
i. Pregnancy testing only required for women of child bearing potential (WOCBP). A positive urine pregnancy test requires confirmation with a serum pregnancy test.
 
j. E-RS: COPD is a subset of EXACT-PRO and is not a separate assessment.
 
k. Rescue medication use will be assessed via e-diary and MDI sensor.
 
l. The Clinic Visit PROactive Physical Activity in COPD tool will be assessed in a subset of approximately 50% of study participants
 
m. Pre-dose PK samples will be collected in all participants at Visits 3, 6, 7, and 10. In a subset of participants (approx. 50 participants at each dose level) at Visit 3, PK samples will be collected at pre-dose, 0.5, 1, 2, 4, 6, 8, 10, 12 hours post-dose. In a subset of participants (approx.. 50 participants at each dose level) at Visit 10, PK samples will be collected at pre-dose, 0.5. 1. 2. 4. 6, 8, 10, 12 hours post-dose.
													

### **14.3. Appendix 3: Assessment Windows**

In general, data will be reported according to the nominal time of clinic visits and assessments as specified in the protocol. For example, if a participant recorded values for the Day 28 visit that were actually made on the 21st day of treatment, they will be presented as Day 28 values in the summary tables.

Participants that withdraw from the study at the time of a scheduled study visit will have data collected in the eCRF as part of the scheduled study visit. In order to collect all questionnaires that are scheduled to be performed at the Early Withdrawal (EW) Visit, eDiary data is reported as an EW Visit. If the date of the EW diary assessment is the same as the date of a scheduled visit date from the eCRF and there is no diary data present at the scheduled visit in question, the EW diary data will be listed, summarized and analysed as part of the scheduled visit (if the diary data was scheduled to be performed at the visit in question).

## 14.4. Appendix 4: Study Phases

### 14.4.1. Study Phases

Assessments and events collected outside scheduled study visits will be classified into study phases according to the time of occurrence relative to the start and/or stop date of study treatment. The ‘worst case-post baseline’ derivation for summaries will consider all scheduled and unscheduled measurements that have been assigned a treatment phase of ‘On-treatment’.

#### 14.4.1.1. Study Phases for Diary Data

Diary data (including EXACT events) treatment states are specified in Section 14.6.3.

#### 14.4.1.2. Study Phases for Concomitant Medication

COPD medication combinations taken at screening will include all COPD medications that were taken on the day of the screening visit, excluding medications that stopped on the day of the screening visit.

Treatment phases for summaries of COPD and non-COPD concomitant medications will be assigned as follows:

Study Phase	Definition
Prior	Medications taken on or before the day before treatment start date defined as: (conmed start date < treatment start date or ‘Taken prior to study?’ is ‘Yes’ or study treatment not started or conmed start date is missing) Note: prior concomitant medication data will only be summarized for COPD medications. All screening data will be listed.
On-treatment	If study treatment stop date > study treatment start date then this includes medications taken between the study treatment start date and study treatment stop date - 1 (inclusive) defined as follows: (conmed start date < study treatment stop date or conmed start date is missing) and (conmed stop date >= study treatment start date or (conmed stop date is completely missing and study treatment start date is non-missing))  If study treatment stop date = study treatment start date then this includes medications taken on the study treatment start date (which is equal to the study treatment stop date) defined as follows. (conmed start date <= study treatment stop date or conmed start date is missing) and (conmed stop date >= study treatment start date or (conmed stop date is completely missing and study treatment start date is non-missing))
Post-treatment	If study treatment stop date > study treatment start date then this includes medications taken after the study treatment stop date defined as follows: (conmed stop date >= study treatment stop date or (conmed stop date is completely missing and study treatment stop date is non-missing)) If study treatment stop date = study treatment start date then this includes medications taken after the study treatment stop date + 1 defined as follows. (conmed stop date > study treatment stop date or (conmed stop date is completely missing and study treatment stop date is non-missing))

**NOTES:**

- A concomitant medication will be classed in every period of the study in which it was taken.
- See Section 14.7.2.1 for handling of partial dates.
- If the study treatment stop date is missing, it will be imputed as described in Section 14.6.1.

**14.4.1.3. Study Phases for Event Data**

Classification of a HCRU exacerbation/AE as having onset on-treatment will be made with reference to the study treatment start and stop dates and the event onset date. If the event onset date is missing, then the event will be considered on-treatment.

Study Phase	Definition
Pre-treatment	If onset date is prior to treatment start date Start Date < Study Treatment Start Date
On-treatment	If onset date is on or after treatment start date & on or before treatment stop date + 3. Study Treatment Start Date ≤ Start Date ≤ Study Treatment Stop Date + 3 days
Post-treatment	If onset date is after treatment stop date + 3. Start Date > Study Treatment Stop Date + 3 days

Note: assume on-treatment unless there is evidence to the contrary

**14.4.1.4. Study Phases for Other Data**

All data collected at scheduled study visits after Day 1 will be considered on-treatment. Any data collected at unscheduled visits (ie, laboratory data, vital signs, ECGs, spirometry, CAT and SGRQ) will be classified as on-treatment based on the study treatment start date (and time, if available) and study treatment stop date and the date (and time, if available) of the visit/assessment. If the visit/assessment date is missing, then the event will be considered on-treatment.

Study Phase	Definition
Pre-treatment	If assessment/visit date (and time) is on or prior to treatment start date (and time) Assessment/Visit Date (and time) ≤ Study Treatment Start Date (and time)
On-treatment	If assessment/visit date (and time) is after treatment start date (and time) & on or before treatment stop date + 3. Study Treatment Start Date (and time) < Assessment/Visit Date (and time) ≤ Study Treatment Stop Date + 3 days
Post-treatment	If assessment/visit date is after treatment stop date + 3. Assessment/Visit Date > Study Treatment Stop Date + 3 days

Note: assume on-treatment unless there is evidence to the contrary

## 14.5. Appendix 5: Data Display Standards & Handling Conventions

### 14.5.1. Reporting Process

Software	

 
The currently supported versions of SAS software will be used.
 
	
Reporting Area	
HARP Server	: uk1salx00175
HARP Compound	: GSK1325756
Analysis Datasets	

 
Analysis datasets will be created according to Legacy GSK A&R dataset standards for the strategic interim and CDISC standards (SDTM IG Version 3.2 & ADaM IG Version 1.1].
 
	
Generation of RTF Files	

 
RTF files will be generated for strategic interim and final reporting efforts
 
	

### 14.5.2. Reporting Standards

General	

 
The current GSK Integrated Data Standards Library (IDSL) will be applied for reporting, unless otherwise stated (IDSL Standards Location: https://spope.gsk.com/sites/IDSLLibrary/SitePages/Home.aspx):             
 
4.03 to 4.24: General Principles
 
5.01 to 5.08: Principles Relating to Data Listings
 
6.01 to 6.11: Principles Related to Summary Tables
 
7.01 to 7.13: Principles Related to Graphics
 
 
 
	
Formats	

 
GSK IDSL Statistical Principle 4.24 for decimal places (DP's) will be adopted for reporting of data based on the raw data collected, unless otherwise stated.
 
Numeric data will be reported at the precision collected on the eCRF.
 
The reported precision from non eCRF sources will follow the IDSL statistical principles but may be adjusted to a clinically interpretable number of DP's.             
 
E-RS: COPD and SGRQ will have a min and max to 1 decimal places (dp) and then follow IDSL standards for reporting other summary statistics.
 
CAT will have a min and max to 0 dp and then follow IDSL standards for reporting other summary statistics.
 
 
 
Categories will be based on rounded values to the precision collected on the eCRF, i.e., categories of % predicted FEV1 will be based on the rounded (to 1 dp) values of the variable FEV1PDPC
 
Summaries of continuous data will include number of participants, mean, SD, median, minimum and maximum and for C-RP and fibrinogen outputs the 25th and 75th percentile.
 
Percentages between 1% and 99%, inclusive, will be rounded to integers. Percentages greater than 0%, but less than 1%, will be reported as <1%, and percentages greater than 99%, but less than 100%, will be reported as >99%.
 
	
Planned and Actual Time	

 
Reporting for tables, figures and formal statistical analyses:             
 
Planned time relative to dosing will be used in figures, summaries, statistical analyses and calculation of any derived parameters, unless otherwise stated.
 
 
 
	


 
Actual time will be used for calculation of times to events and Kaplan-Meier plots.
 
Reporting for Data Listings:             
 
Planned and actual time relative to study drug dosing will be shown in listings (Refer to IDSL Statistical Principle 5.05.1).
 
Unscheduled or unplanned readings will be presented within the participant's listings.
 
 
 
									
Unscheduled Visits									

 
Unscheduled visits will not be included in summary tables and/or figures except as part of a maximum/minimum/worst case post-baseline assessment or if they are assigned as the baseline assessment as detailed in Section 5.2.
 
All unscheduled visits will be included in listings.
 
									
Cardiovascular Event Reports									

 
Laboratory results, ECG results/findings and vital signs measurements collected as part of cardiovascular event reports will not be included in any tables, listings or any minimum/maximum post-baseline assessments.
 
									
Time to Event Results									

 
For all time to event analyses, the first quartile and median time to event will be presented. If less than 25% of participants experienced the event within a treatment group then the first quartile will be displayed as NA (not applicable) for that treatment. If less than 50% of participants experienced the event within a treatment group then the median will be displayed as NA for that treatment.
 
									
Descriptive Summary Statistics									
Continuous Data	Refer to IDSL Statistical Principle 6.06.1								
Categorical Data	N, n, frequency, %								
Graphical Displays									

 
Refer to IDSL Statistical Principals 7.01 to 7.13.
 
									
Seeds for Bayesian Analyses									

 
The seeds used to for the Bayesian analyses were generated using the ranuni function in SAS. The same seeds should be applied for all endpoints and populations.
 
									

  
 Chain	Seed	
   
 1	2619	
 
 2	413	
 
 3	9243	
  
		Chain	Seed	1	2619	2	413	3	9243
Chain	Seed								
1	2619								
2	413								
3	9243								

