4. OBJECTIVES AND ENDPOINTS

Objectives	Endpoints

Primary
 
 • To characterize the dose response of danirixin compared with placebo on the incidence and severity of respiratory symptoms in participants with COPD • To compare the safety of danirixin with placebo in participants with COPD 	
 • Change from baseline in respiratory symptoms measured by E-RS:COPD daily diary at month 6: total score and subscales (i.e. breathlessness, cough and sputum, and chest symptoms) • Adverse events (AE), clinical laboratory values, vital signs, electrocardiogram (ECG)

Objectives	Endpoints

Secondary
 
 • To characterize the dose response of danirixin compared with placebo on the annual rate of moderate/severe COPD exacerbations in participants with COPD • To further characterize the clinical activity of danirixin compared to placebo in participants with COPD 	
 • Healthcare Resource Utilization (HCRU)-defined COPD exacerbations • E-RS:COPD Responder Analysis (including subscales) • Number of Exacerbations of Chronic Pulmonary Disease (EXACT) tool defined events • Time to first EXACT event • EXACT event severity • EXACT event duration for all events • Time to first HCRU-defined COPD exacerbation • Time to first severe HCRU-defined COPD exacerbation • HCRU-defined exacerbation duration • Change from baseline for the St. George's Respiratory Questionnaire (SGRQ) total score (derived from SGRQ-C) • SGRQ responder analysis • Change for baseline COPD Assessment Test (CAT) total score • CAT responder analysis • Lung function (FEV1, FEV1 % predicted, FVC, FEV1/FVC ratio) • Rescue medication use • Participant experience of physical activity (subset of approximately 50% of participants) measured using PROactive Clinic Visit Tool (C-PPAC)

Objectives	Endpoints

 To characterize the pharmacokinetics of danirixin in participants with COPD 	
 Danirixin concentration and standard pharmacokinetic parameters for danirixin (e.g. AUC, Cmax, Tmax), using dried blood spot data

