9.2.5. Cardiovascular and Death Events

For any cardiovascular events detailed in [Appendix 4](#) and all deaths, whether or not they are considered SAEs, specific Cardiovascular (CV) and Death sections of the CRF will be required to be completed. These sections include questions regarding cardiovascular (including sudden cardiac death) and non-cardiovascular death.

The CV CRFs are presented as queries in response to reporting of certain CV MedDRA terms. The CV information should be recorded in the specific cardiovascular section of the CRF within one week of receipt of a CV Event data query prompting its completion.

The Death CRF is provided immediately after the occurrence or outcome of death is reported. Initial and follow-up reports regarding death must be completed within one week of when the death is reported.

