Investigators will be required to fill out the specific CV event page of the CRF for the following AEs and SAEs:

- Myocardial infarction/unstable angina
- Congestive heart failure
- Arrhythmias
- Valvulopathy
- Pulmonary hypertension
- Cerebrovascular events/stroke and transient ischemic attack
- Peripheral arterial thromboembolism
- Deep venous thrombosis/pulmonary embolism
- Revascularization

Recording AE and SAE**AE and SAE Recording**

- When an AE/SAE occurs, it is the responsibility of the investigator to review all documentation (eg, hospital progress notes, laboratory, and diagnostics reports) related to the event.
- The investigator will then record all relevant AE/SAE information in the CRF.
- It is **not** acceptable for the investigator to send photocopies of the participant's medical records to GSK in lieu of completion of the GSK /AE/SAE CRF page.
- There may be instances when copies of medical records for certain cases are requested by GSK. In this case, all participant identifiers, with the exception of the

participant number, will be redacted on the copies of the medical records before submission to GSK.

- The investigator will attempt to establish a diagnosis of the event based on signs, symptoms, and/or other clinical information. Whenever possible, the diagnosis (not the individual signs/symptoms) will be documented as the AE/SAE.

Assessment of Intensity

The investigator will make an assessment of intensity for each AE and SAE reported during the study and assign it to 1 of the following categories:

- Mild: An event that is easily tolerated by the participant, causing minimal discomfort and not interfering with everyday activities.
- Moderate: An event that causes sufficiently discomfort and interferes with normal everyday activities.
- Severe: An event that prevents normal everyday activities. An AE that is assessed as severe should not be confused with an SAE. Severe is a category utilized for rating the intensity of an event; and both AE and SAE can be assessed as severe.

An event is defined as 'serious' when it meets at least 1 of the predefined outcomes as described in the definition of an SAE, NOT when it is rated as severe.

Assessment of Causality

- The investigator is obligated to assess the relationship between study treatment and each occurrence of each AE/SAE.

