**NOTES :**

- The treatment phase definitions specified in Section 14.4.1.4 will be used and only assessments within the on-treatment period will be considered in assessment of minimum/maximum/worst-case post-baseline.
- Assessment of minimum/maximum/worst-case post-baseline will include on-treatment data from scheduled, unscheduled and study treatment discontinuation visits (if applicable)

Laboratory Parameters
------------------------------

General
----------------

- NQ laboratory results will be treated as missing in summary displays. However, the results will be listed as received (e.g. '<x' or '>x').
- If numeric laboratory results are missing but a character result has been recorded, ie. <X, (the numeric part of the character value)/2 will be used to assign the PCI ranges.
- A 'worst case post-baseline' change classification will be derived, in which participants will be counted in the 'to low' and 'to high' categories if they reported a change from an 'in range' baseline to a value below or above the PCI criteria (respectively) at any scheduled or unscheduled on-treatment visit. Participants who did not report a change to a value outside the PCI criteria at any visit after the start of study treatment will be counted in the 'to w/in range or no change' category.

Multiple Measurements for On-Treatment Visits for Safety
---

- Participants having both high and low values relative to PCI criteria at post-baseline visits for safety parameters will be counted in both the high and low categories of the "worst case post-baseline" row of related summary tables.

ECG		
General		

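### SAP 14.5.2 keeps laboratory, ECG and vital-sign values held only on cardiovascular event reports out of every table, listing and extreme-value summary, without a stated reason

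*SAP*

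**What the plan says.** The Cardiovascular Event Reports item in SAP 14.5.2 covers three kinds of data, "Laboratory results, ECG results/findings and vital signs measurements", and rules that those "collected as part of cardiovascular event reports will not be included in any tables, listings or any minimum/maximum post-baseline assessments". It states neither a reason nor an exception.

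Other parts of the SAP set general rules for including data, none of which mentions this carve-out:

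- Just above it, in the same section: "All unscheduled visits will be included in listings".
- Section 14.4.1: the worst-case post-baseline "derivation for summaries will consider all scheduled and unscheduled measurements that have been assigned a treatment phase of" on-treatment.
- The notes in 14.6.4 repeat this for minimum, maximum and worst-case values, naming scheduled, unscheduled and treatment discontinuation visits.
- Section 8 opens by committing to report all collected safety data, in the way it then describes.

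Protocol section 4 makes laboratory values, vital signs and ECG part of the primary safety endpoint, alongside adverse events. Protocol Appendix 4 adds: "Investigators will be required to fill out the specific CV event page of the CRF for the following AEs and SAEs". Its list includes infarction or unstable angina, heart failure, arrhythmias and stroke. Protocol 9.2.5 says that "specific Cardiovascular (CV) and Death sections of the CRF will be required to be completed" for those events and for all deaths.

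**The concern.** The ban applies to data that exist only because an event happened. Only a participant with a triggering event can have values on a cardiovascular event report, so only such participants can lose values. Readings taken around a cardiac event are also the ones a safety reader would most want to see. That they are more often abnormal is a reasonable inference, although the documents do not say so.

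At stake are the outputs built on extremes: the highest QTcF, the worst ECG finding and the worst vital sign. These rest on rare values, so one omitted reading can remove a participant from a category. If events were more frequent in one arm, more readings could be lost from that arm. The ban on listings goes further, because a reviewer could not look up the individual value in any planned output.

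**Working it through.** The point turns on a reporting rule. The plan gives no figure to reproduce, so the check sets the texts against each other.

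**1. Reach of the rule.** It names tables, listings and minimum/maximum assessments. Worst-case summaries are not named, but they are tables and so are covered. Figures are not named either. Those that plot maximum post-baseline values (SAP Figures 3.2 and 3.3) are caught through the minimum/maximum clause.

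**2. Which values are lost.** The rule works by data source. Combining 14.5.2, 14.6.4 and 14.7.1 gives:

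| Where the value is recorded | By-visit summaries | Extreme-value outputs | Listings |
|---|---|---|---|
| Scheduled visit | in | in | eligible |
| Unscheduled or discontinuation visit | generally out | in, if on-treatment | eligible |
| Cardiovascular event report only | out | out | out |

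The gap is the last row.

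**3. Which outputs are affected (SAP Appendix 11, final analysis numbering).**

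- ECG: Table 3.22 (findings), Tables 3.24 and 3.25 (maximum QTcF and maximum increase), Listings 32 to 35, and Listing 59 (QTcF outliers).
- Vital signs: Table 3.27 (worst case) and Listing 36.
- Laboratory: Tables 3.17 and 3.19 (worst case) and Listings 27 to 31.
- The minimum/maximum rows within Tables 3.16, 3.18, 3.23 and 3.26.

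**4. Whether the values appear elsewhere.** Appendix 11 has no display of cardiovascular event report data. Section 14.6.4 defines adverse events of special interest as infective pneumonia only, so there is no cardiovascular grouping. SAP Table 1, which records departures from the protocol's analysis plan, does not mention this exclusion. Protocol 10.5.2 plans to tabulate or plot every safety endpoint.

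**5. Whether scheduled readings fill the gap.** Under the protocol's Schedule of Activities, ECG and vital signs after Day 1 fall on Days 28, 84 and 168, plus early withdrawal. The intervals are 28 − 1 = 27, 84 − 28 = 56 and 168 − 84 = 84 days. A reading at the time of an event will often not coincide with a scheduled one.

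**6. Scale.** Protocol 5.2 plans about 600 randomised participants and 10.3 allocates them equally to six arms: 600 / 6 = 100 per arm. If *k* participants in an arm have their only outlying value on a cardiovascular event report, the arm's outlier proportion is understated by *k*/100, or *k* percentage points. The documents give no basis for *k*. They contain no expected event count, and neither shows which measurements the page collects. The wording of 14.5.2 presupposes that some are collected, but *k* could be zero.

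**The case against.** The case on the other side has real force, and most of it stands.

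- **The exclusion is by source, not by participant.** A reader might infer that no ECG documenting an arrhythmia, or a QTcF above 500 msec at the time of an event, can ever be reported. The documents do not support that. A reading also entered at a scheduled, unscheduled or discontinuation visit stays in. The early withdrawal visit includes an ECG, and SAP 14.7.1 lets that visit count in worst-case assessments.
- **The events are not hidden.** They appear by treatment in the adverse event, serious event, fatal event and discontinuation tables and listings. Under Protocol Appendix 4, an abnormal result that the investigator judges clinically significant is itself an adverse event. What goes missing is the measured value. An adverse event term cannot place a participant in a QTcF category.
- **By-visit means do not change**, because 14.5.2 already keeps unscheduled readings out of them. A reader might infer that a whole arm's safety profile would look falsely close to placebo. Only extremes and listings can change, and a shift towards placebo would also require more affected events on danirixin.
- **It is not a flat contradiction.** A specific exception to a general rule is ordinary drafting, the notes in 14.6.4 speak of visits rather than report pages, and section 8 qualifies its commitment. The weakness is a missing cross-reference and a missing reason.
- **Event-time laboratory values do not belong in the PCI summaries.** SAP 14.8.1 sets its multipliers on the central laboratory's range, and a flag would not repair counts that mix standards.

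The likely rationale is that these readings are less standardised. The SAP does not say so. It could justify keeping such values out of the main summaries. It cannot justify withholding them from listings, where nothing is pooled.

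**Conclusion.** The concern holds in a limited form. The SAP removes collected values of primary safety data types from all planned outputs when they are held only on a cardiovascular event report. It gives no reason and provides no substitute display. The effect is confined to extreme-value outputs and listings.

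Its size cannot be quantified from the documents. The only scale available is about 1 percentage point of an arm's outlier proportion for each affected participant, assuming the planned 100 per arm. The conclusion assumes that some readings exist only on the report page, which 14.5.2 implies but neither document shows. A stronger claim, that the rule conceals a cardiac signal or biases the comparison between doses by a known amount, is not supported.

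**What to change.** 1. In SAP 14.5.2, delete the word *listings* from the exclusion. Add one mITT listing by treatment of all laboratory, ECG and vital-sign values from cardiovascular event reports, flagged by source.
2. Add a supplementary version of the maximum-QTcF, ECG-finding and worst-case vital-sign outputs (Tables 3.22, 3.24, 3.25 and 3.27) that includes on-treatment values from these reports. The main versions stay as planned.
3. Keep laboratory values from these reports out of the PCI summaries and show them in the new listing only.
4. State the reason for any exclusion that remains, and cross-reference it in 14.4.1 and 14.6.4.

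The cost is a change of wording, one listing and a few reruns on data that 14.5.2 treats as already collected. There is a small downside: event-time readings may come from less standardised equipment, and they add measurements only for participants with events. The source flag and the supplementary status of the reruns deal with both.
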